¹ In extremely rare situations, the clinician may complete the Post-Visit 1 Questionnaire on paper. In such scenarios, the paper form should be scanned and uploaded at the [participant documents](#) page, and the answers should be copied into the tracking system by completing the task from the individual participants page. See [instructions for the Parent Post-Visit 1 Questionnaire](#) for comparison.

Page 1

 - Post-Clinic Visit 1 Clinician Survey - Assesment	View Data								
 - Post-Clinic Visit 1 Clinician Survey - AssesmentScales1	View Data								

2. Based on the information you have now, how confident are you in being able to identify the primary causal etiology of the child's condition? (You can check any box along the scale)
 
Not at all Completely
 

0	1	2	3	4	5	6	

		0	1	2	3	4	5	6	
0	1	2	3	4	5	6			

3. What do you think is the chance that this is a genetic condition? (You can check any box along the scale)
 
Definitely not genetic Definitely genetic
 

0	1	2	3	4	5	6	

		0	1	2	3	4	5	6	
0	1	2	3	4	5	6			

4. How likely is it that the diagnostic tests you are ordering for the patient will reveal the cause of the patient's condition? (You can check any box along the scale)
 
Not at all Definitely No testing ordered
 

0	1	2	3	4	5	6	7	

		0	1	2	3	4	5	6	7
0	1	2	3	4	5	6	7		

5. How likely is it that exome sequencing would reveal a diagnosis for this patient? (You can check any box along the scale)
 
Not at all Definitely
 

0	1	2	3	4	5	6	

		0	1	2	3	4	5	6	
0	1	2	3	4	5	6			
Back Next	Save Save & exit								

Page 2

- Post-Clinic Visit 1 Clinician Survey - AssesmentScales2 View Data

6. In an ideal scenario, what do you think would be the most appropriate initial genetic test for this patient? (Check one)

Single gene test
 Multigene panel test
 Exome/genome
 No genetic test

7. To what extent can this patient's symptoms be improved with available treatments? (You can check any box along the scale)

Not at all Completely Not applicable

0	1	2	3	4	5	6	7
---	---	---	---	---	---	---	---

8. How likely is it that learning a diagnosis for this patient will change your clinical management? (You can check any box along the scale)

Not at all Definitely Not applicable

0	1	2	3	4	5	6	7
---	---	---	---	---	---	---	---

9. How likely is it that learning a specific diagnosis for this patient would improve this patient's health outcomes? (You can check any box along the scale)

Not at all Definitely Not applicable

0	1	2	3	4	5	6	7
---	---	---	---	---	---	---	---

Back Next Save Save & exit

[REDACTED] - Post-Clinic Visit 1 Clinician Survey - Caregiver View Data

10. In your opinion, how prepared was the patient's caregiver(s) for today's clinical visit? (Check one)

Not at all prepared
 A little bit prepared
 Very prepared
 Extremely prepared

11. In your opinion, how well did the patient's caregiver(s) understand the information you provided? (Check one)

Not at all
 A little bit
 Somewhat
 Very much
 Completely

12. To what extent was the patient's caregiver(s) prepared to be a partner with the child's care team? (Check one)

Not at all prepared
 A little bit prepared
 Very prepared
 Extremely prepared

13. In your opinion, how likely is it that this patient/caregiver will be fully compliant with medical recommendations? (Check one)

Extremely unlikely
 Very unlikely
 A little bit unlikely
 Equally likely and unlikely
 A little bit likely
 Very likely
 Extremely likely

Back Next Save Save & exit

[REDACTED] - Post-Clinic Visit 1 Clinician Survey - Caregiver2 View Data

14. How would you rate the number of questions asked by the caregiver(s)? (Check one)

Far too many
 A little too many
 Just right
 A little too few
 Far too few

15. To what extent did the caregiver's questions influence the appointment? (Check one)

Very disruptive
 A little disruptive
 Neither disruptive nor conducive
 A little conducive
 Very conducive

16. How would you rate the overall relevance of the caregiver's questions? (Check one)

All or nearly all questions were relevant
 Most questions were relevant
 Some questions were relevant
 Few questions were relevant
 Not applicable

17. Did the caregiver hand you a list of pre-prepared questions during the visit?

No
 Yes

19. Today, were you able to articulate a clear next step to establish a diagnosis? (Check one)

No
 Yes

20. Today, were you able to give the patient a clear recommendation for management of symptoms? (Check one)

No
 Yes
 Not Applicable

Back Next

Save Save & exit

[REDACTED] - Post-Clinic Visit 1 Clinician Survey - Appointment Recommendations 1 View Data

21. Did you order or recommend any of the following for the patient related to today's appointment?

A cytogenetic test (*Check one*)

Karyotype only
 Karyotype and microarray
 Microarray only
 Other
 I did not order/recommend

A molecular genetic test (*Check all that apply*)

Single gene test or small panel test (<10 genes)
 Large panel test (>10 genes)
 Exome sequencing
 Mitochondrial DNA testing
 Other
 I did not order/recommend

A metabolic lab test (*Check all that apply*)

Plasma amino acids
 Urine organic acids
 Acylcarnitine panel
 Lactate
 Ammonia
 Metabolomic panel
 Transferrin isoelectric focusing
 Guanidinoacetate
 I did not order/recommend

An endocrine lab test (*Check all that apply*)

Thyroid
 Diabetes related
 Adrenal axis
 Other
 I did not order/recommend

Back Next

Save Save & exit

[REDACTED] - Post-Clinic Visit 1 Clinician Survey - Appointment Recommendations 2 View Data

21. Did you order or recommend any of the following for the patient related to today's appointment?

An lipids lab test (Check all that apply)

Cholesterol panel
 Other
 I did not order/recommend

A chromosome stability lab test (Check all that apply)

DEB breakage
 Telomere length
 Radiation sensitivity
 Other
 I did not order/recommend

Other lab tests

No Yes

Back Next Save Save & exit

[REDACTED] - Post-Clinic Visit 1 Clinician Survey - Appointment Recommendations 3 View Data

21. Did you order or recommend any of the following for the patient related to today's appointment?

An imaging test (Check all that apply)

MRI with contrast
 MRI without contrast
 CT with contrast
 CT without contrast
 Heart ultrasound/echocardiography
 Ultrasound of other body parts
 Plain films
 I did not order/recommend

Back Next Save Save & exit

Post-Clinic Visit 1 Clinician Survey - Appointment Recommendations 4 View Data

21. Did you order or recommend any of the following for the patient related to today's appointment?

A procedure to obtain a tissue sample for testing (*Check all that apply*)

Muscle biopsy
 Lumbar puncture
 Skin biopsy
 Other
 I did not order/recommend

Prophylactic surgery to reduce disease risk

No Yes

Non-invasive electrophysiology (*Check all that apply*)

EKG
 EEG
 Other
 I did not order/recommend

Invasive electrophysiology (*Check all that apply*)

EMG
 Nerve conduction
 Other
 I did not order/recommend

Referral for therapeutic services (*Check all that apply*)

Speech therapy
 Occupational therapy
 Physical therapy
 Other
 I did not order/recommend

Referral to a non-MD health professional (*Check all that apply*)

Audiology
 Dental
 Other
 I did not order/recommend

Back Next

Save Save & exit

- Post-Clinic Visit 1 Clinician Survey - Appointment Recommendations 5 View Data

21. Did you order or recommend any of the following for the patient related to today's appointment?

Referral to another medical specialty for evaluation or management (Check all that apply)

Cardiology
 Neurology
 Genetics and Metabolism
 Ophthalmology
 Nephrology
 Dermatology
 Pulmonology
 Immunology/Allergy
 Rheumatology
 Hematology
 Oncology
 Other
 I did not order/recommend

Referral for mental health support (Check all that apply)

Mental health
 Social support
 Palliative care
 Other
 I did not order/recommend

Other changes to management (Check all that apply)

Recommended a new medication
 Recommended a change of dose of an existing medication
 Recommended discontinuation of an existing medication
 Changes to over the counter (OTC) medicines or supplements
 Medical/metabolic diet
 General dietary recommendations
 Recommended change in exercise or level of activity
 Other types of lifestyle changes
 Any other recommendations not covered above
 I did not order/recommend

[Back](#) [Next](#) [Save](#) [Save & exit](#)

- Post-Clinic Visit 1 Clinician Survey - Recommendations

[View Data](#)

22. Would the recommendations you listed above in question 21 change if you had the ability to obtain exome sequencing for this patient? (Check one)

No

Yes

Don't know

23. Does this family have access to the resources needed to comply with your recommended course of action? (Check one)

No

Yes

Don't know

24. Did your perception of the family's resources impact the recommendations that you made today? (Check one)

No

Yes

[Back](#) [Next](#) [Save](#) [Save & exit](#)

[REDACTED] - Post-Clinic Visit 1 Clinician Survey - About The Visit		View Data
[REDACTED] - Post-Clinic Visit 1 Clinician Survey - Thank You		View Data
<h2>Thank you for completing the NCGENES Survey!</h2>		
Back	Finish & Finalize	Save Save & exit
<small>(Support group or counseling)</small>		
D. How to explain what the condition means to people outside the family who may need to know (e.g., teachers, social workers)		 Yes  No
E. How to talk to their child about their child's condition		 Yes  No
F. How to talk about the child's condition to other people		 Yes  No
G. The drawbacks of each option for diagnosing this condition		 Yes  No
H. The drawbacks of each option for treating and managing the condition		 Yes  No
I. The benefits of each option for diagnosing the condition		 Yes  No
J. The benefits of each option for treating and managing the condition		 Yes  No
K. Whether relatives may be at risk for this condition		 Yes  No
L. The impact of the condition on other child(ren) or any other child the parent may have		 Yes  No
M. What to expect for the child in the future		 Yes  No
N. How new medical knowledge or treatments that become available may change how this condition affects the child		 Yes  No
26. What was the length of consultation time compared to average? (Check one)		
 Much longer than average		
 A little longer than average		
 Average		
 A little shorter than average		
 Much shorter than average		
Back	Next	Save Save & exit

Questionnaires – Collection Method

1. Begin the “Questionnaires – Collection Method” task by clicking the “Get Started” button next to the task on the individual participant’s page.

14

09/11/2019

Questionnaires - Collection Method (2894)

Pending

Get Started

2. The following dialog box will appear. For each questionnaire, select from the dropdown whether that questionnaire was completed by phone, tablet (or computer), or paper. Once all four questions are answered, click the blue “Finish & Finalize” button to complete the task.

- Questionnaires - Devices

Please select the type of device used to complete the following questionnaires:

1. Baseline/Intake Questionnaire

Select...

2. Pre-Visit 1 Parent Questionnaire

Select...

3. Post-Visit 1 Parent Questionnaire

Select...

4. Post-Visit 1 Clinician Questionnaire

Select...

Select...

Phone

Tablet

Paper

Finish & Finalize

Save

Save & exit

Collect Developmental Age

1. To complete the “Collect Developmental Age” task, click the “Get Started” button next to the task on the individual participant page.

9	11/11/2019	Collect Development Age (3319)	Pending	 Get Started
---	------------	--------------------------------	---------	---

 - Collect Development Age - Collection View Data

Please confirm development age for Last Assent

Select...

[figure not shown]
Finish & Finalize Save Save & exit

2. The following screen will appear. From the dropdown menu, select the developmental age of the participant as provided by the child’s provider.
3. Once the age has been selected, click the blue “Finish & Finalize” button to complete the task.

Randomization to Genome Sequencing

1. To complete the “Randomization to Genome Sequencing” task, click the “Get Started” button next to the task on the individual participant page.

15	09/11/2019	Randomization to Genome Sequencing (2896)	Pending		Get Started
----	------------	---	---------	---	-----------------------------

2. The screen to the right will appear. **This screen is the consent form for this randomization. The user should read through and discuss the form with the parent in detail.**
3. Indicate whether the parent consents for their child’s data to be used in future studies. 
4. If the parent *does not* consent to randomization, click the blue “save” button to complete the task.¹ 
5. The date and time will auto-populate above both signature fields. If the parent consents, direct them to sign in the appropriate gray box. 
6. Record the parent’s name, their relationship to the participant, and the participant’s name in the appropriate boxes below the signature.
7. Sign and print your name in the second set of boxes.
8. Click the blue “save” button to complete the task.

University of North Carolina at Chapel Hill
Consent to Participate in a Research Study
Consent Form 1: Randomization to Research Genomic Sequencing
Child Participants
Biomedical Form

IRB Study # 17-0316
Consent Form Version Date: 02-28-2018
Title of Study: North Carolina Clinical Genomic Evaluation by Next-gen Exome Sequencing, phase 2 (NCGENES 2)
Principal Investigators: [name], PhD, [name]., PhD, [name].
UNC-Chapel Hill Department: Genetics
UNC-Chapel Hill [contact]
Email Address: [contact]
Funding Source: National Human Genome Research Institute at National Institutes of Health
Study Contact: [name]
Study Contact [contact] (toll free)

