B. Get the facts about the options for my child's future health care	Not at all confident	0	1	2	3	4	Very confident
C. Understand information that is given to me by the healthcare team	Not at all confident	0	1	2	3	4	Very confident
D. Ask my child's healthcare team questions without feeling judged	Not at all confident	0	1	2	3	4	Very confident
E. Express my concerns about each choice the healthcare team offers for my child's care	Not at all confident	0	1	2	3	4	Very confident
F. Ask my child's healthcare team for advice	Not at all confident	0	1	2	3	4	Very confident
G. Let my child's healthcare team know what I think is best for my child	Not at all confident	0	1	2	3	4	Very confident

Page 2 of 11

Back Next Save Save & exit

- Pre-Clinic Visit 1 Survey - Childs Visit View Data

Your Child's Clinic Visit

3. How prepared do you feel to take part in the appointment today? (Check one)

Not at all prepared
A little bit prepared
Very prepared
Extremely prepared

4. Do you have specific questions in mind that you plan to ask the doctor today? (Check one)

No, I do not have any questions
No, I have questions but I don't plan to ask them
Yes, I have a few questions I plan to ask
Yes, I have a lot of questions I plan to ask

Page 3 of 11

Back Next Save Save & exit

██████████ - Pre-Clinic Visit 1 Survey - How You Feel View Data

How You Feel

5. Over the last 2 weeks, how often have you been bothered by the following problems? Please check one box to tell us how often you have experienced each thing listed below.

A. Feeling nervous, anxious or on edge	Not at all	Several days	More than half the days	Nearly every day
B. Not being able to stop or control worrying	Not at all	Several days	More than half the days	Nearly every day
C. Worrying too much about different things	Not at all	Several days	More than half the days	Nearly every day
D. Trouble relaxing	Not at all	Several days	More than half the days	Nearly every day
E. Being so restless that it is hard to sit still	Not at all	Several days	More than half the days	Nearly every day
F. Becoming easily annoyed or irritable	Not at all	Several days	More than half the days	Nearly every day
G. Feeling afraid as if something awful might happen	Not at all	Several days	More than half the days	Nearly every day
H. Little interest or pleasure in doing things	Not at all	Several days	More than half the days	Nearly every day
I. Feeling down, depressed, or hopeless	Not at all	Several days	More than half the days	Nearly every day

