A. Get the facts about my child's condition Not at all confident (0) 1 2 3 Very confident (4)

B. Get the facts about the options for my child's future health care Not at all confident (0) 1 2 3 Very confident (4)

C. Understand information that is given to me by the healthcare team Not at all confident (0) 1 2 3 Very confident (4)

D. Ask my child's healthcare team questions without feeling dumb Not at all confident (0) 1 2 3 Very confident (4)

E. Express my concerns about each choice Not at all confident (0) 1 2 3 Very confident (4)

F. Ask my child's healthcare team for advice Not at all confident (0) 1 2 3 Very confident (4)

G. Let my child's healthcare team know what I think is best for my child Not at all confident (0) 1 2 3 Very confident (4)

Back Next Save Save & exit

[REDACTED] - Intake Survey - HealthcareandYourFamily View Data

Healthcare and Your Family

23. How long have you been searching for an answer to your child's symptoms?

24. Has there been any time in the last 12 months when you wanted or needed your child to see a doctor or health care professional and did not?

No
 Yes

25. In the past 3 months, how much work have you missed because of your child's condition or treatments? (Check one)

None
 Less than a week
 Between 1 and 4 weeks
 Between 4 and 8 weeks
 Between 8 and 12 weeks
 I stopped working altogether

26. In the past 3 months, how much did your child's condition or treatments make it hard to finish your normal work (including both work outside of the home and housework)? (Check one)

Not at all
 A little bit
 Somewhat
 Quite a bit
 Very much

[Back](#) [Next](#) [Save](#) [Save & exit](#)

██████████ - Intake Survey - HealthcareandYourFamilyPageTwo View Data

27. Please read each statement below and check the box that indicates your response as it applies to the past 7 days.

A. I know that I have enough money in savings, retirement, or assets to cover the cost of my child's treatment. Not at all A little bit Somewhat Quite a bit Very much

B. My out-of-pocket medical expenses are more than I thought they would be. Not at all A little bit Somewhat Quite a bit Very much

C. I worry about the financial problems I will have in the future as a result of my child's condition or treatment. Not at all A little bit Somewhat Quite a bit Very much

D. I feel I have no choice about the amount of money I spend on care. Not at all A little bit Somewhat Quite a bit Very much

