K. Whether my relatives may be at risk for this condition Yes No

L. The impact of the condition on my other child(ren) or any other child I may have Yes No

M. What to expect for my child in the future Yes No

N. How new medical knowledge or treatments that become available may change how this condition affects my child Yes No

Page 7 of 10

Back Next Save Save & exit

View Data

Talking to Others

Sometimes parents want or need to talk to other people about their child's diagnostic tests. These questions will help us understand the ways talking to others might be hard for parents.

16. How confident are you in explaining diagnostic testing to others? Please check one box for each person listed below.

I feel confident that I can explain diagnostic testing to:

A. My child	Not at all confident	A little confident	Somewhat confident	Very confident	Not applicable
-------------	----------------------	--------------------	--------------------	----------------	----------------

B. My other children	Not at all confident	A little confident	Somewhat confident	Very confident	Not applicable
----------------------	----------------------	--------------------	--------------------	----------------	----------------

C. My family members	Not at all confident	A little confident	Somewhat confident	Very confident	Not applicable
----------------------	----------------------	--------------------	--------------------	----------------	----------------

D. My child's teachers or therapists	Not at all confident	A little confident	Somewhat confident	Very confident	Not applicable
--------------------------------------	----------------------	--------------------	--------------------	----------------	----------------

E. Other doctors or specialists that treat my child	Not at all confident	A little confident	Somewhat confident	Very confident	Not applicable
---	----------------------	--------------------	--------------------	----------------	----------------

17. How confident are you in explaining the kinds of diagnostic tests your child is having to others? Please check one box for each person listed below.

I feel confident that I can explain diagnostic testing to:

A. My child	Not at all confident	A little confident	Somewhat confident	Very confident	Not applicable
-------------	----------------------	--------------------	--------------------	----------------	----------------

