B. My other children	Not at all confident	A little confident	Somewhat confident	Very confident	Not applicable
----------------------	----------------------	--------------------	--------------------	----------------	----------------

C. My family members	Not at all confident	A little confident	Somewhat confident	Very confident	Not applicable
----------------------	----------------------	--------------------	--------------------	----------------	----------------

D. My child's teachers or therapists	Not at all confident	A little confident	Somewhat confident	Very confident	Not applicable
--------------------------------------	----------------------	--------------------	--------------------	----------------	----------------

E. Other doctors or specialists that treat my child	Not at all confident	A little confident	Somewhat confident	Very confident	Not applicable
---	----------------------	--------------------	--------------------	----------------	----------------

18. How stressful would it be to do following things? Please check one box for each person listed below.

How stressful would it be to:

A. Explain what diagnostic testing is to other people?	Not at all stressful	A little stressful	Somewhat stressful	Very stressful
--	----------------------	--------------------	--------------------	----------------

B. Explain the kinds of diagnostic tests your child is having to other people?	Not at all stressful	A little stressful	Somewhat stressful	Very stressful	Not applicable
--	----------------------	--------------------	--------------------	----------------	----------------

C. Explain what steps other family members should take to learn whether they are at risk for a health problem like your child's?	Not at all stressful	A little stressful	Somewhat stressful	Very stressful	Not applicable
--	----------------------	--------------------	--------------------	----------------	----------------

Page 8 of 10

[Back](#) [Next](#) [Save](#) [Save & exit](#)

Page 9

[REDACTED] - Post-Clinic Visit 1 Survey - Childs Provider View Data

Your Child's Provider(s)

19. How often have you experienced these things when getting care for your child at this clinic? Please check one box next to each statement. Your responses will be kept confidential.

A. My child's provider(s) explained things in a way that was easy to understand.	Never	Sometimes	Usually	Always
B. My child's provider(s) listened carefully to me.	Never	Sometimes	Usually	Always

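### Post-visit Question 17 asks about the child's own tests but carries Question 16's answer stem, so its five items are ambiguous; confidence items D and E also differ between the intake and pre-visit screens and need checking

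*Protocol*

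**What the plan says.** **Post-Visit 1 Parent Questionnaire, Talking to Others.** The general question is "16. How confident are you in explaining diagnostic testing to others". The next one is "17. How confident are you in explaining the kinds of diagnostic tests your child is having to others". Under each, the line that the parent completes is "I feel confident that I can explain diagnostic testing to". The same five targets follow both times (the child, other children, family members, teachers or therapists, other doctors), with the same response options. On the same survey page, Question 18 keeps the two ideas apart. Its item A is "A. Explain what diagnostic testing is to other people", and its item B asks about the kinds of tests this child is having.

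**Seven-item confidence scale, each item scored 0 to 4.** It appears as Question 22 of the Baseline Intake screens and as Question 2 of the Pre-Visit 1 Parent Questionnaire screens. Items A, B, C, F and G match. Item D reads "D. Ask my child's healthcare team questions without feeling dumb" at intake and "D. Ask my child's healthcare team questions without feeling judged" at pre-visit. Item E reads "E. Express my concerns about each choice" at intake and "E. Express my concerns about each choice the healthcare team offers for my child's care" at pre-visit.

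**How the forms are completed.** Parents normally fill in the post-visit survey themselves in clinic on the tablet. Intake is usually completed on paper before Visit 1 and keyed in by staff, with the tablet as a fallback. Mailing 2 states that the intake survey is the same whatever the pre-visit prep assignment.

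**The concern.** Two parents can answer Question 17 honestly and mean different things. One reads the numbered question and rates confidence in explaining this child's tests. The other reads the stem beside the answer boxes and rates confidence in explaining testing in general, as in Question 16. The data do not show which reading was used. Question 18 shows that the authors intended two constructs, so the Question 17 stem looks like an uncorrected copy.

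On the confidence scale, intake and pre-visit lie either side of the pre-visit materials: the reminder-call script asks parents to finish the intake survey before looking at the rest of the packet. A reader is likely to compare the two scores. If D and E were fielded with different wording, part of any movement from intake to pre-visit would reflect the wording. Both items lie close to what the question prompt list is meant to encourage, namely asking questions and voicing concerns. Feeling dumb and feeling judged are also not synonyms: the first is about oneself, the second about others' opinion.

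Item wording is fixed in the instrument, so an analysis plan could not remove either ambiguity from the responses.

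**Working it through.** The protocol gives no sample size, effect size or scoring rule for these measures, so there is no stated figure to reproduce. The check is a comparison of texts and a short piece of algebra.

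**Questions 16 and 17**

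| Element | Question 16 | Question 17 |
|---|---|---|
| Numbered lead | diagnostic testing in general | kinds of tests this child is having |
| Stem completed by the parent | "I feel confident that I can explain diagnostic testing to" | identical |
| Targets A-E and response options | five people | identical |

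The leads differ and everything beneath them is the same. All 5 of the 5 Question 17 items inherit the conflict.

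**Confidence scale**

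1. An item-by-item comparison of intake Question 22 with pre-visit Question 2 finds 2 of 7 items different (D and E): 2/7 = 28.6%.
2. The maximum total is 7 × 4 = 28.
3. Let the rewording move each affected item by *s* points with no true change. The protocol gives no value for *s*, so a range is assumed. Within-arm change on the total moves by 2*s*, and on the item mean by 2*s*/7:

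| *s* per item (assumed) | Shift on 0-28 total | Shift on item mean |
|---|---|---|
| 0.1 | 0.2 | 0.029 |
| 0.25 | 0.5 | 0.071 |
| 0.5 | 1.0 | 0.143 |

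4. Between arms, let the true mean changes be Δ₁ and Δ₀. With the same shift in both arms, (Δ₁ + 2*s*) − (Δ₀ + 2*s*) = Δ₁ − Δ₀, so the arm difference moves by 0 at every value of *s*.
5. If the wording effect differed by arm (*s*₁ and *s*₀), the arm difference in change would move by 2(*s*₁ − *s*₀). Nothing in the protocol indicates such a difference: the intake form is common to both arms, and only one pre-visit form is shown.
6. What can remain in the arm comparison is a lower correlation between intake and pre-visit scores, hence some loss of precision if intake is used as a covariate. The protocol gives no correlation from which to size this.

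**The case against.** **Is Question 17 simply a duplicate of Question 16?** A reader might infer that it is, or that it cannot be interpreted at all. The documents do not support that. Its numbered lead names the child's own tests directly after a general question, and an attentive parent can tell the two apart. The defect is a lead and stem that disagree. Reporting Question 17 separately is not ruled out, provided that the conflict is stated.

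**Is a trial outcome or change score compromised?** A reader might infer this from the repeated scale. The protocol names neither set of items as an outcome and defines no total, change score or covariate for them. The analysis plan is not at hand.

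**Is the D/E difference established?** Not for most parents. The intake pages printed in the protocol are those used to key in a paper form. The paper versions are age-specific, are kept elsewhere and are not reproduced, so the short item E could be an abbreviated entry label. The protocol's illustrations may also not all be current: the distress alert section places the anxiety items at pre-visit Question 6, while the screen shows them at Question 5. Against this, the intake screens carry paper-style instructions such as circling a response, and some parents may complete intake on the tablet. The difference is therefore plausible and worth checking, but unconfirmed.

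**Does the rewording bias the randomised comparison?** Not if its effect is common to both arms, as the algebra shows. Nor must a baseline covariate match the follow-up item word for word. Removing D and E from the covariate would discard 2 of 7 baseline items to repair something that does not bias the arm difference.

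**Conclusion.** The Question 17 point holds. On the form as shown, all five items have a lead and a stem that ask different things, and parents normally read this form themselves. How many parents answered the stem rather than the lead is unknown, so the degree of overlap with Question 16 cannot be sized from the documents.

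The D/E point holds conditionally. The two screens differ on 2 of 7 items. Whether most parents saw that difference depends on the paper intake form. If they did, within-arm change on the 0-28 total is shifted by 0.2 to 1.0 points under the assumed 0.1 to 0.5 points per item, and the correlation with baseline may fall somewhat. The between-arm difference is unaffected as long as the shift is the same in both arms.

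Both are instrument-wording faults that are cheap to correct. Neither shows that a trial result is invalid.

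**What to change.** 1. **Question 17.** Keep the opening of the stem and replace its object, so that it asks about explaining *the kinds of diagnostic tests my child is having*. Record the form version with each response. Wherever Question 17 data collected before the edit are reported, state that the lead and stem conflicted.
2. **Items D and E.** Compare the paper intake form, in every age version and version date used, with the fielded pre-visit form. If the wording differs, use identical text in both.
3. **Data already collected, if the difference is confirmed.** Keep the full seven-item intake score as the baseline covariate, if one is used. Add a five-item score (A, B, C, F, G) as a sensitivity analysis of within-arm change from intake to pre-visit.

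The cost is one stem edit, a document check, up to two item edits with a new survey date, and a version indicator in the data. The task lists already show version labels for these surveys, so the indicator is a small addition. The drawback is that responses before and after an edit are not strictly interchangeable and must remain distinguishable.
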